Specifically, PrEP Romania is a hybrid in-person + mobile health (mHealth) program that facilitates PrEP uptake and adherence by providing knowledge, motivation, and support. mHealth is an ideal HIV-prevention strategy for Romanian GBM given its private accessibility in stigmatizing locales. The study will integrate and adapt for Romania two tools we developed and tested in the US 1) SPARK, an in-person intervention for uptake of and adherence to PrEP using brief sex-positive motivational counseling; and 2) P3 (Prepared, Protected, emPowered), a PrEP adherence support app that utilizes engaging social networking and game-based elements, while an in-app portal allows for individualized live text-based adherence counseling to heighten GBM's sense of accountability, enhance their motivation, and address specific adherence needs. These goals will be accomplished in collaboration with a Romanian Partner Consortium of GBM-competent health providers, including: infectious disease physicians (IDPs), whom we trained in GBM-affirmative practice; community-based organizations (CBOs); and the National Institute of Infectious Diseases (NIID) and Romanian Association against AIDS (ARAS), prominent HIV-focused medical institutions. This study has two aims.

Aim 1. Conduct a randomized controlled trial (RCT) to test the early efficacy of PrEP Romania. The US team will make necessary adjustments to PrEP Romania with the Romanian Partner Consortium. These adjustments are based on a pilot study conducted prior to the award of the current study by NIH, between September 2020 and March 2022. Then, 120 PrEP-eligible

GBM in two cities (Bucharest and Cluj-Napoca) will be randomized to receive either 1) PrEP Romania (counseling, self-directed app use, and in-app text-based adherence support for 6 months) or 2) a PrEP education condition. We will examine differences across arms in PrEP uptake, adherence, persistence (self-reported and via dried blood sample biomarkers), and mediators (self-efficacy, mental health) at 3- and 6-months post-PrEP initiation.

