Aim 2. Explore implementation outcomes to prepare for a future multi-city effectiveness trial. The team will identify individual and institutional barriers to and facilitators of implementing PrEP Romania by applying Proctor et al.'s implementation framework to the analysis of RCT's feasibility and acceptability data, and PrEP counselor, IDP, clinic administrator, and GBM interviews. Results will inform a future effectiveness-implementation hybrid trial of a scaled-up PrEP Romania across several cities.

Research Aims & Abstracts

Hypotheses: Compared to control arm (education only), PrEP Romania participants (counseling, self-directed app use, and in-app text-based adherence support for 6-mos) will be more likely to accept PrEP (H₁); evince better adherence (H₂); and sustain PrEP use across 6-mos (H₃).

STUDY DESIGN

One hundred and twenty GBM will enroll in a 2-arm pilot to test PrEP Romania's (a) feasibility (medical visit attendance), (b) acceptability (intervention staff and GBM interviews about counseling and app usability), and (c) PrEP uptake (filled prescriptions), adherence (self-reported and DBS) and persistence (still on PrEP) at 3- and 6-month follow-ups.

Study Sites: Two of Romania's primary infectious disease (ID) centers in Bucharest and Cluj-Napoca will serve as the study sites. Their IDPs are involved in our ongoing research and treat GBM who test positive for HIV/STIs through our study. They, together with their site psychologists, were part of the team's pilot study for the current RCT, which ended in March 2022.

The National Institute of Infectious Diseases (NIID) Bucharest Clinic. The largest ID university hospital in Romania, NIID is one of 9 regional centers monitoring HIV. NIID monitors all HIV/AIDS cases in Romania, and oversees the other 8 regional centers.

The Cluj-Napoca Clinic. The Regional Center of Evidence and Monitoring of HIV Infection Cluj-Napoca (CREM Cluj) covers 5 jurisdictions in northern Romania. A total of 706 HIV/AIDS patients are registered in CREM Cluj, with 668 being on ART.

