Screening: Within the study ad, potential participants will click on a link to complete a 5-min eligibility screener on Qualtrics, a HIPAA-compliant secure web application. The first page in the screener consists of the informed consent form for screening eligibility. This form is self-administered and contains the researchers' contacts that can be used for clarification purposes. Once potential participants have read through the electronic consent form and agree to screen for eligibility, they will click "Yes" on the consent form, if still interested in taking the screener (or "No" otherwise, and exit). Should the consent to screen, the next screen will take them to the first questions of the screener. Eligible GBM will have the option to provide contact information at the end of the screener, in a separate survey, to be contacted for consent.

Consent: Eligible participants will be contacted within days of screening to undergo the phone consent process we used successfully in other studies. Specifically, ARAS staff will send potential participants a link to an electronic Qualtrics-based consent form. ARAS staff and participants will read the electronic consent document together while on the phone (15 minutes). Points of confusion will be clarified and interested participants will submit the electronic consent. The consenting ARAS staff will submit their own version of the Qualtrics-based electronic consent form.

Assessments: Upon consent, participants will be sent their unique study ID an electronic link to a Qualtrics-based baseline survey (30 minutes). They will complete similar 3- and 6-month surveys, and 20% will complete exit interviews with the PI about their intervention experiences to inform future PrEP Romania iterations.

Procedures: After the baseline survey is completed, participants will be randomized 1:1 to receive PrEP Romania (n=60) or an Education Condition (n=60). Next, research staff will help participants schedule their first visit with the clinic for PrEP counseling, biological testing and PrEP prescription pick-up. All participants will be tested at the clinic for HIV at each visit, and, if positive, treated immediately.

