PrEP initiation, and then every 6 weeks. Participants can ask questions about PrEP and health through the app, which will be answered by the trained research team. The entire follow-up period will be 6 months. At the first 1-hr visit, the PrEP counselor will deliver the in-person component PrEP Romania regarding motivation for PrEP uptake, and if applicable, adherence. The counselor will help GBM download the app, and demonstrate each feature, answer all questions and provide a guided tour. Participants will be encouraged to explore all app components routinely and be told that the counselors will contact them periodically through the app messaging system to discuss adherence facilitators and barriers. Next, participants will meet for 1-hr with the IDP, who will discuss requisite lab results and reinforce PrEP-related facts. The IDP will next provide a prescription to all GBM interested in starting PrEP, to be filled at the co-located clinic pharmacy, provided for free through the study. A follow-up clinic visit will occur 3- and 6-months after initial visit. Reported PrEP side-effects will be carefully monitored and, if necessary, PrEP use will be discontinued. In a pilot study for this RCT by this team, no participants reported side-effects. Appbased Support. GBM will be encouraged to use the app daily for adherence reminders, information, and socialization. The PrEP counselor will contact GBM via the app two weeks post-PrEP initiation for a 15-min adherence coaching session using adapted SPARK language to reinforce daily adherence and trouble-shoot barriers. Participants may message their counselor with questions, including for technical assistance, to be answered within 24 hrs.

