### **3.4 Timing of Outcome Assessments**

Outcomes measured at baseline, 3 months, and 6 months post-randomization.

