## **Secondary Outcomes**

The secondary outcomes include continuous DBS PrEP adherence, self-reported PrEP adherence (binary and continuous), PrEP knowledge (binary: all questions answered correctly vs. not), PrEP motivation (ordinal categorical), PrEP attitudes and beliefs (continuous), PrEP barriers, PrEP facilitators (continuous), PrEP stigma (continuous), anxiety symptomology (continuous), depression symptomology (continuous), STI diagnoses in the last 6 months (binary: any vs. none), and number of condomless anal sex (CAS) acts with HIV-positive or unknown-status partners in the last 6 months (continuous). For all secondary outcomes, missing data will be recorded and addressed.

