### **Secondary Outcomes**

The secondary outcomes include continuous, binary, and categorical variables, each analyzed with an appropriate link function based on the outcome type. For continuous outcomes, such as depression and anxiety symptomology scores, an identity link function will be used, estimating the intervention effect as the difference in mean scores between groups. This model will be implemented using the "lmer()" function in R. Binary secondary outcomes, will use the same logit link function and implementation details as the primary outcome analysis.

**Table 1.** List of secondary outcomes.

Variable coding
Continuous
Binary and continuous
Continuous
Continuous
Binary
Ordinal categorical, with 7 categories

PrEP stigma	Continuous
Positive attitudes/beliefs	Continuous
about PrEP	
Negative attitudes/beliefs	Continuous
about PrEP	
PrEP barriers	Continuous
PrEP facilitators	Continuous
STI diagnoses	Binary
CAS acts	Continuous

Each model will output the intervention effect at baseline, 3 months, and 6 months (with the exception of STI diagnoses and CAS acts, which are only measured at baseline and 6 months as well as DBS and self-report PrEP adherence, which are only measured at 3 months and 6 months), with 95% confidence intervals to provide estimates of precision.

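### The six-month look-back for STI diagnoses, timed from randomisation, takes in the first clinic visit; if STIs are tested there, infections acquired before any intervention can count as follow-up events

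*SAP*

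**What the plan says.** SAP 6.1 lists, as a secondary outcome, "STI diagnoses in the last 6 months (binary: any vs. none". SAP 6.2 says that this outcome is not collected at 3 months: "STI diagnoses and CAS acts, which are only measured at baseline and 6 months". SAP 3.4 fixes the time origin: "Outcomes measured at baseline, 3 months, and 6 months post-randomization".

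The protocol (Study procedures, Procedures) gives the order of events: "After the baseline survey is completed, participants will be randomized 1:1 to receive PrEP Romania (n=60) or an Education Condition (n=60". After that, "research staff will help participants schedule their first visit with the clinic for PrEP counseling, biological testing and PrEP prescription pick-up". Counselling and app set-up, and physician education in the control arm, begin at that first visit (Intervention Arm and Control Arm descriptions). SAP 3.2 agrees with this order, because it enlarges the randomisation sequence to allow for exclusions after the initial medical visit.

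The assays at the first visit are not listed. HIV is the only test named for every visit. The indirect sign of STI testing is under Study Sites, where the site physicians, described as involved in the team's ongoing research, are said to "treat GBM who test positive for HIV/STIs through our study".

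The protocol uses other time origins for follow-up. Aim 1 places outcomes "at 3- and 6-months post-PrEP initiation", and the intervention description says "A follow-up clinic visit will occur 3- and 6-months after initial visit".

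**The concern.** An infection detectable at the first visit was acquired before the man received anything from either arm. The baseline survey comes too early to record a diagnosis made at that visit. A six-month look-back from six months after randomisation does reach it, and no text excludes it. Such a diagnosis would be scored as a follow-up event that the intervention could not have prevented.

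Events of this kind add the same expected amount to both arms and so dilute the contrast. The baseline-outcome term that SAP 6.2 lists among the fixed effects would not correct this if the baseline value comes from the survey, because that value predates the test. The trial is meant to inform a larger one, so an attenuated estimate matters even where a significance test would be uninformative.

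**Working it through.** **Reach of the window under each time origin**

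| Origin of the 6-month assessment | Source | Position of the first visit |
|---|---|---|
| Randomisation | SAP 3.1, 3.4 | Inside the look-back |
| Initial clinic visit | Protocol, Study procedures | At its edge |
| PrEP initiation | Protocol, Aim 1 | At or near its edge |

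**The plan's own figures.** There is none for STIs. The only computed design figure is the standardised effect in SAP 3.3, 0.06 / 0.32 = 0.1875, which rounds to the stated 0.19. It concerns adherence and has no bearing here.

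**Model.** Let p be the probability of a first-visit diagnosis that falls in the window, the same in both arms, and q the probability of a later diagnosis, independent of the first. Then

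P(counted) = 1 − (1 − p)(1 − q)

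difference in counted risk = (1 − p)(q_intervention − q_control).

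**Inputs.** From the documents: 60 per arm, two-sided alpha 0.05, and retention of about 89% (60 × 0.89 ≈ 53 per arm). Assumed, because the documents give no STI rates: q = 20% in control and 10% in intervention, with p from 0 to 20%.

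**Example, p = 5%.** Control: 1 − 0.95 × 0.80 = 0.240. Intervention: 1 − 0.95 × 0.90 = 0.145. Odds ratio: (0.145 / 0.855) / (0.240 / 0.760) = 0.54.

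**Power.** Two-proportion normal approximation: Φ[(|d| − 1.96·SE0) / SE1], with SE0 from the pooled proportion and SE1 from the separate ones. At p = 0 and 60 per arm: SE0 = √(2 × 0.15 × 0.85 / 60) = 0.0652, SE1 = √((0.16 + 0.09) / 60) = 0.0645, and (0.100 − 0.1278) / 0.0645 = −0.43, which gives 33%.

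| p | Control | Intervention | Difference (points) | Odds ratio | Power, 60 per arm | Power, 53 per arm |
|---|---|---|---|---|---|---|
| 0 | 20.0% | 10.0% | −10.0 | 0.44 | 33% | 30% |
| 5% | 24.0% | 14.5% | −9.5 | 0.54 | 26% | 23% |
| 10% | 28.0% | 19.0% | −9.0 | 0.60 | 21% | 19% |
| 20% | 36.0% | 28.0% | −8.0 | 0.69 | 15% | 14% |

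**Sensitivity to the assumed rates**

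- 30% control, 15% intervention: odds ratio 0.41 at p = 0, then 0.47, 0.52 and 0.60 at p = 5%, 10% and 20%.
- An increase, 15% control, 25% intervention: 1.89 at p = 0, then 1.69, 1.57 and 1.42. The pull is toward 1 in either direction.
- Partial capture, with 30% against 15% and 15% of men positive at the first visit: 0.56 if all of these fall in the window, 0.50 if half do, 0.41 if none do.
- Equal later rates: the counted rates are also equal, so nothing is diluted.

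**The case against.** A reader might infer that the outcome, as written, does count infections found at the first visit and is therefore known to be biased. The documents do not support that, for three reasons.

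- **Testing.** STI testing at that visit is an inference. Only HIV is named, and the Study Sites sentence may refer to the team's wider research rather than to this trial's first visit.
- **Data source.** The SAP does not say whether the STI outcome is self-reported or laboratory-based, nor that its baseline value comes from the survey. If first-visit results already serve as the baseline value, much of the problem disappears.
- **Time origin.** On the protocol's two origins the visit lies at or near the edge of the window, so capture could depend on the survey date and on recall.

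Nor would every man positive at the first visit move from none at baseline to any at follow-up. A recent bacterial STI is one route to eligibility, and those men may already be positive at baseline.

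Two further points stand. Equality of p across arms holds only in expectation. Chance imbalance with 53 to 60 per arm could move a single estimate either way, and detection requires attending a visit that follows unmasked randomisation. Also, nothing in the documents supports a halving of STI risk. The hypotheses concern PrEP acceptance, adherence and persistence, and the control-arm education states that PrEP itself does not protect against STIs.

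These points limit how firmly and how large the problem can be stated. They do not remove it, because the SAP's stated window and time origin include the visit and nothing excludes what is found there.

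**Conclusion.** The point holds conditionally. On the SAP's own timing, the STI look-back includes a visit that precedes all intervention content. If STIs are tested there and those diagnoses reach the outcome, the expected bias is toward no difference, by the factor (1 − p) on the risk difference.

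The size cannot be derived from the documents. Under the assumed 20% and 10%, the difference falls from 10.0 points to between 9.5 and 8.0 for p of 5% to 20%, with the odds ratios shown in the table. It is nil if first-visit STI testing is not done, if those diagnoses fall outside the window, or if there is no true effect.

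This is one of many secondary outcomes in a pilot. Its power is about 50% at best in the scenarios tried, even undiluted (30% against 15%, 60 per arm), and the primary outcome is untouched. The change is still worth making, because it replaces a stated window with a less biased one at little cost.

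**What to change.** - Define the 6-month STI outcome as any STI diagnosed after the first clinic visit, not counting infections found by testing at that visit, and word the survey item to match. If the survey is already fielded, remove first-visit positives using clinic records.
- State whether the outcome is self-reported, laboratory-based or both, and whether the first visit includes STI tests. If it does not, saying so settles most of the point.
- Reconcile the SAP's randomisation origin with the protocol's PrEP-initiation and initial-visit origins.
- State which window applies to men who never attend the first visit, since the primary analysis follows intention to treat.
- Report first-visit positives descriptively by arm. Using them in the baseline covariate is optional: they are measured after randomisation in an unmasked trial and are missing for men who do not attend.

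The cost is one SAP definition, one survey item and, if the survey has been fielded, a check of clinic records. The downside is slightly fewer counted events in an outcome whose power is low in any case.

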#### 6.2 Analysis Methods

We will use Generalized Linear Mixed Models (GLMMs) to handle the various types of outcomes across primary and secondary measures, which allows for fixed effects (intervention, site, time, baseline outcome, the interaction between intervention and time baseline covariates) and random effects (including participant-level variability). The adjusted covariates include age, relationship status, and PrEP usage. All analyses will be conducted in R. The general form of the GLMM is:

$$g(\mu(Y_{ij})) = \beta_1 I(Time_{ij} = 3) + \beta_2 I(Time_{ij} = 3) \times Intervention + \beta_3 I(Time_{ij} = 6) + \beta_4 I(Time_{ij} = 6) \times Intervention + \beta_5 Covariates_i + \mu_i + \epsilon_{ij}$$

 $Y_{ij}$  represents the outcome for participant i at time j,  $\mu(Y_{ij})$  is the expected value of  $Y_{ij}$  given the covariates,

g(.) is the link function that relates the linear predictors to the expected value of outcome (e.g., logit link for binary outcomes, identity link for continuous outcomes),

 $\beta_1$  is the effect of time at 3 month,

 $\beta_2$  is the interaction effect between intervention and time at 3 month,

 $\beta_3$  is the effect of time at 6 month,

 $\beta_4$  is the interaction effect between intervention and time at 6 month,

 $\beta_5$  is the covariate effect,

 $\mu_i$  is the random intercept for each participant, where  $\mu_i \sim N(0, \sigma_i^2)$ ,

I(.) is the indicator function.

### Treatment effects from the model

3 month	6 month
$eta_2$	$eta_4$

Then the average treatment effect is

$$\frac{\beta_2 + \beta_2}{2}$$

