# 3.3 Sample Size

The Prepare Romania trial's sample size was chosen to provide preliminary data on the hypothesized intervention outcomes, PrEP adherence and persistence among GBMSM in Romania, as well as to inform the design of a future effectiveness trial. A formal power calculation was not conducted due to the exploratory nature of this pilot study. Instead, we followed guidance from Whitehead et al., which provides recommendations for sample sizes in pilot studies.

The sample size of 60 participants per arm (120 total) was selected based on conservative effect size estimates drawn from previous studies evaluating PrEP adherence interventions. In a comparable RCT testing the SPARK intervention, protective PrEP levels (defined as adherence of ≥4 doses per week) were observed in 94% of the intervention arm and 85% of the control arm at the 3-month follow-up, with corresponding rates of 92% and 86% at 6 months. This difference in adherence rates translates to an estimated effect size of 6%, with a pooled standard deviation of approximately 0.32, yielding a standardized effect size of 0.19. Whitehead et al. suggest a minimum sample size of 25 participants per condition for pilot trials when the effect size falls between 0.1 and 0.3. To ensure adequate power, the Prepare Romania trial conservatively enrolls 60 participants per arm, exceeding this minimum and allowing for a robust assessment of intervention impact.

Each site (Bucharest and Cluj-Napoca) is tasked with recruiting 60 participants. With this sample size, the study expects retention at 6 months to exceed 25 participants per arm, even accounting for potential attrition. This estimate is supported by high retention rates (approximately 89%) reported in prior SPARK trials.

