# 4. Statistical Principles

#### 4.1 Confidence Intervals and P-Values

For the Prepare Romania trial, statistical analyses will be conducted with a two-sided significance level set at 0.05. This alpha level applies to all primary and secondary outcomes, ensuring that results are interpreted consistently across study endpoints. The 95% confidence intervals will be calculated for the primary and other key secondary outcomes.

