# 6. Analysis

#### **6.1 Outcome Definitions**

# **Primary Outcome**

The primary outcome of this study is PrEP adherence, which will be measured objectively using dried blood spot (DBS) testing to detect levels of tenofovir diphosphate (TFVdp). Adherence is defined as achieving a TFVdp concentration of ≥1000 fmol/punch, corresponding to a mean dosing frequency of at least four doses per week. This measure will be evaluated at 3- and 6-months post-randomization. The binary operationalization of this measure will serve as the primary outcome.

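### SAP 6.2 prints the average treatment effect as (β2 + β2)/2, which is the 3-month effect alone: very probably a subscript slip, with limited consequence

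*SAP*

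**What the plan says.** The primary outcome is binary PrEP adherence by dried blood spot. SAP 6.1 fixes its timing: "This measure will be evaluated at 3- and 6-months post-randomization". SAP 6.2 gives one mixed-model equation for all outcomes. In it, β2 multiplies the product of the 3-month indicator and intervention, and β4 the matching product at 6 months; of β4 the SAP says that it "is the interaction effect between intervention and time at 6 month".

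Under the heading on treatment effects from the model, a small table puts β2 under 3 months and β4 under 6 months. The next line reads "Then the average treatment effect is", followed by (β2 + β2)/2. No other section of the SAP or protocol gives a formula for the average.

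For reporting, SAP 6.2 also says "Each model will output the intervention effect at baseline, 3 months, and 6 months", with 95% confidence intervals. It exempts dried-blood-spot and self-reported adherence from the baseline output because they are measured only at 3 and 6 months. The average is not in that list.

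**The concern.** An average over two follow-up visits should draw on both. The printed expression uses the 3-month coefficient twice and the 6-month coefficient not at all.

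A SAP is what programmers code from and what readers later check results against. If the formula were followed to the letter, a number labelled as the average over follow-up would hold no 6-month effect. The output would look plausible: a valid estimate with a valid interval, but for a different quantity. It would mislead whenever the intervention effect changes between the visits, which is when an average and a single-visit effect differ.

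**Working it through.** **What the printed formula equals.** The model equation has no separate intervention term, so β2 is the whole intervention effect at 3 months and β4 the whole effect at 6 months, each on the link scale.

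- As printed: (β2 + β2)/2 = β2. The weights are 1 on month 3 and 0 on month 6.
- Equal-weight average of the two tabulated effects: (β2 + β4)/2.
- Difference, printed minus average: β2 − (β2 + β4)/2 = (β2 − β4)/2.

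The difference is zero if β2 = β4, positive if the effect shrinks from 3 to 6 months, and negative if it grows.

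**Variance.** Coded literally, the interval would use Var(β2). The average needs [Var(β2) + Var(β4) + 2Cov(β2, β4)]/4. The covariance term matters because the same participants contribute at both visits.

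**Illustration of size.** The SAP states no numerical value for the average, so there is no figure to reproduce. The only visit-specific rates in the documents are the planning rates in SAP 3.3, from an earlier trial of the counselling component: 94% against 85% at 3 months, "with corresponding rates of 92% and 86% at 6 months".

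- 3 months: odds 0.94/0.06 = 15.667 and 0.85/0.15 = 5.667. Odds ratio 2.765, log odds ratio 1.017.
- 6 months: odds 0.92/0.08 = 11.500 and 0.86/0.14 = 6.143. Odds ratio 1.872, log odds ratio 0.627.
- Printed formula: (1.017 + 1.017)/2 = 1.017, odds ratio 2.76.
- Average of both visits: (1.017 + 0.627)/2 = 0.822, odds ratio 2.28.
- Error: (1.017 − 0.627)/2 = +0.195 on the log scale, a factor of exp(0.195) = 1.22 on the odds ratio.

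If the visits are swapped, so that the effect grows over time, the error is −0.195: the printed formula gives 1.87, while the average is still 2.28.

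These are crude odds ratios. The SAP model gives covariate-adjusted, participant-specific ones, so the figures show the order of size and do not predict this trial's result.

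**The case against.** **It may be a reading artefact.** The table just above the formula has lost characters in the machine-read text, so a misread subscript cannot be excluded. This stands as a reason to look at the source PDF. It is not evidence of a misreading: the table symbols lost their leading characters but kept subscripts 2 and 4, and the longer model equation kept β1 to β5 intact.

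**It is an obvious slip.** With both coefficients defined and tabulated directly above, only one average makes sense, and few analysts would code a term averaged with itself. This also stands, and it lowers the likelihood of harm. It does not make the printed formula right.

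**Little depends on it.** The 3-month and 6-month effects are reported separately, so the point estimate of the average can be recovered from them. No sample size or stated decision rests on the average. In the illustration the shift is modest against the noise. With 60 per arm and no dropout, the crude standard error of the 3-month log odds ratio is √[1/(60 × 0.94 × 0.06) + 1/(60 × 0.85 × 0.15)] = √(0.2955 + 0.1307) = 0.653, and 0.195/0.653 = 0.30. The SAP itself stresses the "exploratory nature of this pilot study". All of this stands, and it is why the severity is low.

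**A stronger reading is tempting.** A reader might infer that the primary analysis omits 6-month data. The documents do not support that: β4 is in the model and is reported with its own interval. A reader might also infer that the 3-month, 6-month and average effects are three chances at significance, because SAP 4.1 says of the 0.05 level: "This alpha level applies to all primary and secondary outcomes". No section says that any one significant contrast would count as success, so an inflated error rate cannot be attributed to the plan. Which contrast is primary is a different question from this formula.

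**Conclusion.** Wrong as written, low severity. By the SAP's own definitions, the expression given for the average treatment effect is the 3-month effect, with no weight on the 6-month coefficient. The algebra needs no assumption beyond the printed subscript being correct, which the source PDF can settle.

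The consequence is conditional on literal coding. The mislabelled quantity would then differ from the true average by (β2 − β4)/2, in a direction that cannot be known in advance. The 2.76 against 2.28 illustration rests on crude rates from another trial and assumes that the effect declines between visits as it did there. The visit-specific effects remain correct either way, so this is an error in one derived summary and not a flaw in the model or the primary outcome.

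**What to change.** Check the subscript against the source PDF. If it reads as here, replace the formula by (β2 + β4)/2 and add its variance, [Var(β2) + Var(β4) + 2Cov(β2, β4)]/4. With the multiple imputation in SAP 6.3, compute the average and this variance in each of the 15 imputed datasets and pool them by Rubin's rules, as for the other estimates. For binary outcomes, exponentiate the pooled average; the result is the geometric mean of the two visits' odds ratios.

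The cost is one subscript and one or two lines of text. No data, visits or model terms change. If analysis code already exists, confirm that its contrast puts weight one half on each of β2 and β4.
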